3.9.1 Gastrointestinal Inflammation/Diarrhea

In Amgen Study #20101262, 6 subjects treated with ACP-319 developed colitis, including 2 serious cases determined to be of infectious origin (enterocolitis and *Clostridium difficile*). Four cases of Grade 2 or Grade 3 colitis without infectious etiology occurred in subjects treated with 400 mg QD. AEs of colitis resolved with dose reductions of ACP-319 to lower dose levels (200 to 300 mg) in subjects in the 400-mg dose group.

Other studies of PI3K δ inhibitors have recommended that for subjects who develop persistent diarrhea, causes related to concomitant medications or GI infection should be considered and eliminated. Depending upon the clinical circumstances, endoscopy and biopsy may be warranted. In such subjects, after drug discontinuation and resolution of symptoms, rechallenge with PI3K δ inhibitors has resulted in recurrence of symptoms in some but not all subjects and has not been associated with other severe AEs. Subjects

Protocol: ACE-LY-001

have responded well to administration of enteric corticosteroids (e.g., budesonide) or sulfasalazine (AZULFIDINE®) while continuing on PI3K δ inhibitors.

Thus, depending upon the type and severity of the initial GI event, rechallenge with study drug and appropriate support care may be warranted if continued drug administration offers the potential for clinical benefit (Table 3-2). Administer appropriate antibiotics, including vancomycin and/or metronidazole if required for *C difficile* infections. Subjects should be advised to report any new or worsening abdominal pain, onset of fever, chills, nausea, or vomiting.

3.9.2 Elevated Liver Function Tests and Immune-Mediated Hepatitis

In subjects with lymphoid malignancies, reversible serum ALT/AST elevations have been observed (Furman et al. 2010, Kahl et al. 2010) with idelalisib. In these subjects, onset has typically occurred within 2 to 16 weeks of starting the PI3Kδ inhibitor therapy.

Among subjects receiving ACP-319 with Grade 1 to 2 ALT/AST abnormalities, continued dosing has been possible; transaminase values commonly resolve despite continued PI3K δ inhibitor treatment. For those with Grade 3 to 4 ALT/AST elevations, drug interruption has resulted in resolution over 2 to 6 weeks. Successful rechallenge at lower dose levels of PI3K δ inhibitor has been achieved in most subjects. Thus, in subjects with uncomplicated hepatic laboratory abnormalities, the instructions in Table 3-2 should be followed in an attempt to maximize the potential that subjects who appear to be benefiting can continue with study drug treatment.

In selected subjects who experience more complicated hepatic AEs, further workup may be warranted, particularly in subjects who first experience a serum ALT/AST elevation ≥12 weeks from the start of study drug therapy, who have an elevation in serum bilirubin concentration or change in coagulation parameters, or who have other characteristics that suggest a change in liver function. Further workup may include the following: obtaining a history of recent symptoms/illnesses and of relevant past history (e.g., history of hepatitis or of hepatitis A or hepatitis B vaccination); obtaining information regarding concomitant drug use (prescription and nonprescription medications, dietary supplements, alcohol, illicit drugs, special diets); questioning the subject regarding potential exposure to environmental toxins; ruling out viral hepatitis A, B, C, D (if hepatitis B is positive), and E, Epstein-Barr virus, CMV, autoimmune hepatitis, alcoholic hepatitis, nonalcoholic steatohepatitis, hypoxic/ischemic hepatopathy, and biliary tract disease; obtaining additional tests to evaluate liver function (e.g., prothrombin time [PT], activated partial thromboplastin time, international normalized ratio [INR], albumin); and

Protocol: ACE-LY-001

considering gastroenterology or hepatology consultation (Food and Drug Administration. Guidance for industry. Drug-induced liver injury: premarketing clinical evaluation. 2009 Jul). Hepatic AEs that require additional workup should be discussed with the medical monitor.

Hepatitis has been reported in subjects treated with the combination of acalabrutinib and ACP-319. Subjects with hepatitis should be carefully monitored, and dose modification or interruption of either acalabrutinib or ACP-319 or both may be indicated. Refer to Table 3-2 for additional information on management of hepatic AEs.

Subjects should be monitored for increases in liver biochemistry indicating potential Hy's law (PHL) or Hy's law (HL). The investigator is responsible for determining whether a subject meets PHL criteria at any point during the study. The process to be followed in identifying and reporting cases of PHL and HL is summarized in Appendix 6.

3.10 CONCOMITANT THERAPY

3.10.1 Permitted Concomitant Therapy

Anti-emetics are permitted if clinically indicated. Standard supportive care medications are permitted as per institutional standards.

For subjects considered at risk for tumor lysis syndrome: Administer appropriate hydration and allopurinol or rasburicase per institutional standards before initiating treatment.

For subjects at risk for pneumonitis: In selected subjects (e.g., those with a history of recurrent pneumonias), anti-infectious prevention should be considered. Initiation of antibiotic prophylaxis against pneumocystis infection (e.g., with trimethoprim-sulfamethoxazole, dapsone, aerosolized pentamidine, or atovaquone) beginning before study drug administration may be warranted. Such supportive care may also offer the benefit of reducing the risk for other bacterial infections (Stern et al. 2014). Prophylaxis with intravenous Ig may be appropriate in subjects with low Ig levels (Raanani et al. 2009). Local practices or guidelines regarding infection prophylaxis may be followed.

For subjects at risk for infections: Bacterial/viral/fungal prophylaxis is allowed per institutional standards.

Protocol: ACE-LY-001

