- 24. Requires treatment with proton-pump inhibitors (e.g., omeprazole, esomeprazole, lansoprazole, dexlansoprazole, rabeprazole, or pantoprazole). Subjects receiving proton-pump inhibitors who switch to H2-receptor antagonists or antacids are eligible for enrollment to this study.
- 25. Total bilirubin >1.5 x upper limit of normal (ULN), or aspartate aminotransferase (AST) or alanine aminotransferase (ALT) >3.0 x ULN.
- 26. Serum amylase >1.5 x ULN or serum lipase >1.5 x ULN.

Protocol: ACE-LY-001

27. Presence of a GI ulcer diagnosed by endoscopy within 3 months before screening.

- 28. Concomitant use of medicines known to cause QT prolongation or Torsades de pointes within 7 days of starting study drug (see Appendix 2).
- 29. Active cytomegalovirus (CMV) infection (positive CMV immunoglobulin [Ig] M and/or positive PCR result).

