3.10.2 Prohibited or Restricted Concomitant Therapy

Any chemotherapy, immunotherapy, kinase inhibitors, bone marrow transplant, experimental therapy, or radiotherapy for treating lymphoid cancer are prohibited.

Localized, short courses of radiotherapy are allowed for the treatment of lesions unrelated to the disease under study, if approved by the medical monitor.

Warfarin or equivalent vitamin K antagonists (e.g., phenprocoumon) are prohibited.

At study entry, subjects may be using topical or inhaled corticosteroids or low-dose steroids (≤10 mg of prednisone or equivalent per day) as therapy for comorbid conditions but use of corticosteroids as therapy of the lymphoid cancer is not permitted. During study participation, subjects may also receive systemic or enteric corticosteroids at any required dosage as needed for treatment-emergent comorbid conditions such as treatment-emergent colitis or pneumonitis.

Use of omeprazole, esomeprazole, lansoprazole, or any other proton-pump inhibitors is prohibited at study entry. The decision to treat with proton-pump inhibitors during the study is at the investigator's discretion, with an understanding of the potential benefit to the subject's GI condition and a potential risk of decreased exposure to acalabrutinib.

Subjects should avoid the use of calcium carbonate-containing drugs or supplements for a period of at least 2 hours before and at least 2 hours after taking acalabrutinib. Although the effect of H2-receptor antagonists (such as famotidine or ranitidine) on acalabrutinib absorption has not been evaluated, if treatment with an H2-receptor antagonist is required, the H2-receptor antagonist should be taken approximately 2 hours after an acalabrutinib dose.

The concomitant use of strong inhibitors/inducers of CYP3A (see Appendix 3) should be avoided when possible. If a subject requires short-term treatment with a strong CYP3A inhibitor (such as anti-infectives for up to 7 days), interrupt acalabrutinib treatment. Conversely concomitant administration of a strong inducer of CYP3A has the potential to decrease exposure of ACP-319 or acalabrutinib and could reduce the efficacy of the study drugs. For additional information on drugs with potential drug-drug interactions, refer to Section 3.11.3.

Use of medications known to prolong QTc interval or that may be associated with Torsades de pointes (see Appendix 2) are prohibited within 7 days of starting study drug and during Day 1 to 28 inclusive of Cycle 1.

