3.10.4 Required Concomitant Medications

Serious and fatal infections have occurred with idelalisib (a drug similar to ACP-319) including opportunistic infections such as *Pneumocystis jirovecii* pneumonia (PJP) and CMV (ZYDELIG [Summary of Product Characteristics]). Therefore, due to possible risk of class effects, prophylaxis for PJP in accordance with local guidelines and institutional standards should be administered to all subjects throughout ACP-319 treatment, and for a period of 2 to 6 months after the last dose of ACP-319. The duration of post-treatment prophylaxis should be based on clinical judgment and may take into account a subject's risk factors such as concomitant corticosteroid treatment and prolonged neutropenia. CMV testing will be required for subjects receiving ACP-319 treatment (see Section 4.1.24).

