4.1.9 Electrocardiogram

A centralized cardiac safety monitoring laboratory will be used in this study to assess the potential of acalabrutinib and ACP-319 as evaluated by ECG measurement of the QTc interval.

Toxicity grading of QTc interval prolongation will be defined by CTCAE and provided in Table 4-1.

Table 4-1. QTc Toxicity Grading Defined by CTCAE

| Grade | Definition |
|-------|--------------------------------------------------------------------------------------------------------------------------------------------------|
| 1 | QTc 450 to 480 ms |
| 2 | QTc 481 to 500 ms |
| 3 | QTc ≥501 ms on at least 2 separate ECGs |
| 4 | QTc ≥501 ms or >60 ms change from baseline or Torsades de pointes or polymorphic ventricular tachycardia or signs/symptoms of serious arrhythmia |

Abbreviations: CTCAE = Common Terminology Criteria for Adverse Events; ECG = electrocardiogram.

The service provider will provide the ECG equipment (12-lead surface), instructions, and training (when requested). Subjects should be in supine position and resting for ≥10 minutes before study-related ECGs. At screening, results from the central ECG reader (triplicates taken at least 1 minute apart) will be averaged to determine eligibility and must meet the eligibility criteria of QTc ≤480 ms. Thereafter, single ECGs are done at each timepoint (Table 4-2). However, if a machine-read ECG registers a QTc (either Bazett's or Fridericia's) of ≥501 ms or >60 ms above baseline then a second ECG must be done after 5 minutes. If at any point, a subject experiences a Grade ≥3 QTc prolongation according to the machine on site (i.e., the subject has 2 consecutive ECGs taken ≥5 minutes apart with a QTc that is ≥501 ms, demonstrate a >60-ms change from baseline, or show other ventricular dysrhythmias per Table 4-1), ACP-319 must be held pending acquisition of the QTc results from the centralized review. If centralized review confirms both ECG QTc readings are ≥501 ms, show a >60 ms change from baseline, or show other ventricular dysrhythmias per Table 4-1, then the subject should have the ACP-319 held until those abnormalities resolve to baseline values and receive any further ACP-319 at a reduced dose level. Conversely, if the centralized review shows that both ECG QTc readings are ≤500 ms and the change in QTc is ≤60 ms from baseline, dosing may be restarted at the same dose level, but missed doses will not be made up.

Protocol: ACE-LY-001

Table 4-2. ECG Acquisition Times

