Appendix 2. Risk Factors for Drug-induced Torsades de Pointes

History of congenital long QT syndrome

Baseline QTc prolongation (>450 ms)

Hypokalemia (potassium ≤3.0 mEq/L)

Severe hypomagnesemia (magnesium ≤1.2 mEq/L)

Bradycardia (resting heart rate <55 beats per minute)

Current or recent past use (within 7 days before study entry) of drugs known to prolong QTc interval and may be associated with Torsades de Pointes (listed below):

amiodarone, amitriptyline, arsenic, astemizole, bepridil, chloroquine, chlorpromazine, ciprofloxacin, cisapride, clarithromycin, desipramine, disopyramide, dofetilide, dolasetron, domperidone, doxepin, droperidol, erythromycin, fluoxetine, gatifloxacin, halofantrine, haloperidol, ibutilide, imipramine, indapamide, itraconazole, ketoconazole, levofloxacin, levomethadyl, mesoridazine, methadone, moxifloxacin, pentamidine, pimozide, probucol, procainamide, procainamide, quetiapine, quinidine, quinidine, risperidone, sertraline, sotalol, sparfloxacin, sumatriptan, terfenadine, thioridazine, venlafaxine, ziprasidone, zolmitriptan,

This list is not exhaustive and new information regarding drugs with dysrhythmic potential emerges on a regular basis. Please refer to the following site (or similar sites) for additional information on drugs with dysrhythmic potential:

http://www.credible meds.org.

Protocol: ACE-LY-001

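### Section 3.10.1 offers aerosolized pentamidine as prophylaxis begun before study drug, while exclusion 28, Section 3.10.2 and Appendix 2 together prohibit pentamidine around the start of treatment

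*Protocol*

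**What the plan says.** Four places in the protocol bear on the point.

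- **Section 3.10.1 (permitted therapy).** For selected subjects at risk of pneumonitis, it names four example agents for pneumocystis prophylaxis: "e.g., with trimethoprim-sulfamethoxazole, dapsone, aerosolized pentamidine, or atovaquone) beginning before study drug administration may be warranted". It also gives two class-wide permissions: "Anti-emetics are permitted if clinically indicated" and "Bacterial/viral/fungal prophylaxis is allowed per institutional standards". None of these refers to Section 3.10.2 or to QT risk.
- **Section 3.10.2 (prohibited or restricted therapy).** Drugs that prolong QTc or may be associated with Torsades, with reference to Appendix 2, "are prohibited within 7 days of starting study drug and during Day 1 to 28 inclusive of Cycle 1".
- **Exclusion 28 (Section 3.3.2, repeated in the Synopsis).** A subject is ineligible for "Concomitant use of medicines known to cause QT prolongation or Torsades de pointes within 7 days of starting study drug", again with reference to Appendix 2.
- **Appendix 2.** The drug list contains the run "methadone, moxifloxacin, pentamidine, pimozide", with no qualification by route.

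Two further sections give the context. Section 3.10.4 says that PJP prophylaxis "should be administered to all subjects throughout ACP-319 treatment", with the agent left to local guidelines. Section 4.1.9 sets up central ECG review of QTc for both study drugs. If that review confirms a qualifying QTc finding, "the subject should have the ACP-319 held until those abnormalities resolve to baseline values", and any further ACP-319 is given at a reduced dose level.

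**The concern.** A site that picks pentamidine from the examples in Section 3.10.1, starts it in the week before treatment and continues it as prophylaxis has followed one section and broken another. On the wording of exclusion 28, its subject is also ineligible. The protocol does not say which text governs.

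The period matters statistically because it is when the QTc question is examined most closely. QTc is a real question here: Section 1.13.2 reports a trend towards QTcF prolongation in the 400-mg cohort of the first-in-human ACP-319 study, although no value exceeded 500 msec and no increase exceeded 60 msec. If some Cycle 1 ECGs were recorded under a listed co-medication, a QTc summary that ignores this cannot separate its effect from that of the study drugs.

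**Working it through.** **1. Is the same drug offered and prohibited at the same time?**

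- Offered: aerosolized pentamidine, beginning before study drug (3.10.1). Section 3.10.4 extends PJP prophylaxis over the whole of ACP-319 treatment, so prophylaxis also covers Cycle 1 for subjects on the combination.
- Prohibited: Appendix 2 drugs within 7 days of starting (exclusion 28 and 3.10.2) and on Cycle 1 Days 1 to 28 (3.10.2).
- Listed: pentamidine, with no route stated (Appendix 2). No other section exempts the aerosolized form.

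The periods overlap and the drug is the same, so the texts conflict. The other three agents named in 3.10.1 (trimethoprim-sulfamethoxazole, dapsone, atovaquone) are not named in Appendix 2, so the direct conflict concerns one of four examples.

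**2. Do the class-wide permissions conflict in the same way?**

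Appendix 2 lists drugs that would fall under them: dolasetron, domperidone and droperidol (anti-emetics); ciprofloxacin, levofloxacin and moxifloxacin (antibacterials); itraconazole and ketoconazole (antifungals). But 3.10.1 names none of these. A general permission followed by a section of specific prohibitions can be read as limited by it. That leaves an ambiguity, because 3.10.1 does not point to 3.10.2.

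**3. How much of the ECG schedule lies in the window? (Table 4-2)**

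- Cycle 1: Day 1 has 5 readings, Day 8 has 5, and Days 15, 22 and 28 have 1 each: 5 + 5 + 3 = 13.
- The Day 1 predose reading precedes treatment, so 13 − 1 = 12 follow the first dose.
- Later: Cycle 2 has 2, Cycles 3 to 6 have 4, and Cycles 9 and 12 have 2: 2 + 4 + 2 = 8.
- Total after first dose: 12 + 8 = 20. Share in the window: 12/20 = 60%.

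**4. Could the DLT decision be affected?**

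The inputs are 6 subjects per cohort, escalation on at most 1 DLT and suspension on 2 or more (Section 3.5). Only ACP-319-related events count, and Grade 3 or higher QTc prolongation is not among the exceptions (Section 3.7).

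Suppose one subject has a co-medication QTc event wrongly counted as a DLT and would otherwise have had none. The decision changes only if exactly one of the other five has a true DLT, with probability 5p(1 − p)⁴, where p is the true DLT rate. The protocol gives no p, so the values below are assumptions:

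- p = 0.05: 5 × 0.05 × 0.95⁴ = 0.20
- p = 0.10: 5 × 0.10 × 0.90⁴ = 0.33
- p = 0.20: 5 × 0.20 × 0.80⁴ = 0.41
- p = 0.30: 5 × 0.30 × 0.70⁴ = 0.36

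These figures apply only once such a misattribution has happened. The protocol gives nothing from which to estimate how often it would.

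**The case against.** The strongest reply is that this is a wording clash over one drug, with safeguards around it and little future effect.

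- **Only an example.** Pentamidine is one option for selected subjects, 3.10.4 leaves the PJP agent to local guidelines, and the medical monitor confirms eligibility before enrolment (Section 3.3.4). This limits how often the clash arises but does not remove it.
- **Causality rules.** Appendix 4 supports an answer of not related when an event may be due to other therapy, and mandatory safety teleconferences precede each next cohort (Section 3.14). A reader might infer that any QTc event under permitted co-medication becomes a DLT, or that one such event stops escalation. The documents support neither: the event must be judged ACP-319-related, and suspension needs a second DLT.
- **The restriction ends after Cycle 1.** A reader might call this an error and say that Appendix 2 drugs are unrestricted from Cycle 2. It is a stated choice that matches the DLT period and the dense ECG sampling. Some listed drugs also remain restricted as CYP3A inhibitors: clarithromycin, itraconazole and ketoconazole as strong, ciprofloxacin and erythromycin as moderate (Section 3.11.3, Table 3-3, Appendix 3).
- **Holding ACP-319 regardless of cause.** The QTc rule in 4.1.9 has no causality step, but a safety rule need not have one.
- **Largely past.** Under Amendment 6 all active subjects receive acalabrutinib monotherapy, and Appendix 5 schedules only cycles beyond 12 and follow-up. No future Part 1 cohort or ACP-319 hold is therefore in prospect. This stands, and it moves the value of the correction from conduct to interpretation.
- **Detail for the SAP.** How ECGs are flagged can properly be left to the SAP, and its absence from the protocol is no fault. The flag is offered as a cheap consequence of the conflict.

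**Conclusion.** The contradiction stands for pentamidine, the only drug named on both sides. It bears on eligibility and on the period that contains the DLT assessment and 12 of the 20 ECGs scheduled after the first dose. The conclusion rests on two readings: that an Appendix 2 entry without a route covers every route, and that prophylaxis begun before study drug continues into Cycle 1, as 3.10.4 implies. The broader permissions in 3.10.1 need a cross-reference and no more.

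Any effect on QTc results depends on how many ECGs were recorded under a listed drug, which the protocol cannot show. The documents do not establish that the QTc evaluation or the DLT count was in fact contaminated. The point remains worth settling because Amendment 6 keeps all the conflicting texts and Section 5.4.1 provides for ECG results to be tabulated and summarised.

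**What to change.** 1. Reconcile Sections 3.10.1 and 3.10.2, exclusion 28 (with its copy in the Synopsis) and Appendix 2, so that no drug is both offered and prohibited in the same window. Which rule applies, and whether route matters, is for the sponsor to decide and state.
2. Add a cross-reference from 3.10.1 to 3.10.2, so that the class-wide permissions are visibly subject to the prohibition.
3. When the ECG data are summarised, flag each post-dose ECG taken while an Appendix 2 drug is recorded, and show QTc with and without the flagged readings. Section 4.1.4 already collects concomitant medications from 21 days before the first dose to 30 days after the last.
4. If any QTc event was counted as a DLT in Part 1, check retrospectively whether an Appendix 2 drug was recorded at the time.

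The cost is a few lines of wording, one derived flag, one extra table and at most a short look back at individual cases. No new procedure or data collection is needed.

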3.10.2 Prohibited or Restricted Concomitant Therapy

Any chemotherapy, immunotherapy, kinase inhibitors, bone marrow transplant, experimental therapy, or radiotherapy for treating lymphoid cancer are prohibited.

Localized, short courses of radiotherapy are allowed for the treatment of lesions unrelated to the disease under study, if approved by the medical monitor.

Warfarin or equivalent vitamin K antagonists (e.g., phenprocoumon) are prohibited.

At study entry, subjects may be using topical or inhaled corticosteroids or low-dose steroids (≤10 mg of prednisone or equivalent per day) as therapy for comorbid conditions but use of corticosteroids as therapy of the lymphoid cancer is not permitted. During study participation, subjects may also receive systemic or enteric corticosteroids at any required dosage as needed for treatment-emergent comorbid conditions such as treatment-emergent colitis or pneumonitis.

Use of omeprazole, esomeprazole, lansoprazole, or any other proton-pump inhibitors is prohibited at study entry. The decision to treat with proton-pump inhibitors during the study is at the investigator's discretion, with an understanding of the potential benefit to the subject's GI condition and a potential risk of decreased exposure to acalabrutinib.

Subjects should avoid the use of calcium carbonate-containing drugs or supplements for a period of at least 2 hours before and at least 2 hours after taking acalabrutinib. Although the effect of H2-receptor antagonists (such as famotidine or ranitidine) on acalabrutinib absorption has not been evaluated, if treatment with an H2-receptor antagonist is required, the H2-receptor antagonist should be taken approximately 2 hours after an acalabrutinib dose.

The concomitant use of strong inhibitors/inducers of CYP3A (see Appendix 3) should be avoided when possible. If a subject requires short-term treatment with a strong CYP3A inhibitor (such as anti-infectives for up to 7 days), interrupt acalabrutinib treatment. Conversely concomitant administration of a strong inducer of CYP3A has the potential to decrease exposure of ACP-319 or acalabrutinib and could reduce the efficacy of the study drugs. For additional information on drugs with potential drug-drug interactions, refer to Section 3.11.3.

Use of medications known to prolong QTc interval or that may be associated with Torsades de pointes (see Appendix 2) are prohibited within 7 days of starting study drug and during Day 1 to 28 inclusive of Cycle 1.

Protocol: ACE-LY-001

